4.0 DRUG/DEVICE INFORMATION

4.1 Not applicable.

5.0 SELECTION AND WITHDRAWAL OF SUBJECTS

- 5.1 Inclusion Criteria: Inclusion criteria for the baseline/screening interview are (1) recent injection of illicit drugs (past 30 days), as verified by checking for venipuncture marks,⁸⁴ (2) age 18 years or older, and (3) ability to provide informed consent.
- 5.2 Exclusion Criteria: Less than 18 years of age, no evidence of recent drug injection, inability to provide informed consent, and non-English speaking.
- 5.3 Withdrawal Criteria: Participants who unable to complete either the experimental or control condition intervention may be asked to withdraw from the study. Each participant will be given at least 2 opportunities to complete the one-hour educational session to which they were assigned.

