2.0 OBJECTIVES AND PURPOSE

To achieve these aims, people who inject drugs (PWID) who report having initiated someone or having injection initiation social learning risks in the past 6 months (N=1,076) will be randomly assigned to receive CTC or an equal attention control condition in Los Angeles (LA) and San Francisco (SF), CA. Injection initiation

and injection initiation social learning variables will be collected at baseline, 6 months, and 12 months. CTC is brief, easy to implement, and novel in its focus on active PWID as a conduit for preventing injection initiation. If proven efficacious, CTC will be a much-needed, practical approach to preventing drug injection initiation.³⁹⁻⁴³

The main outcomes by Aim are as follows: 1) Counts of non-injectors initiated into drug injection at 6 and 12 months; 2) Counts of request to initiate a non-injector into drug injection at 6 and 12 months; and 3) Counts of noninjectors initiated into drug injection and request to initiate non-injectors at 6 and 12 months. The study will be implemented in 2 phases. Phase 1 involves adaptation and training of intervention personnel and Phase 2 involves implementing the full study.

Elucidation goals are to better understand issues related to 1) HAV/HCV effects and 2) drug effects and withdrawal and symptoms management PWID.

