3.9. Baseline interviewing. Baseline interviews will be conducted in English using computer assisted personal interview. The interview will occur in an one-on-one session with a trained research interviewer. Participants will receive \$15 for completing the screening interview. We will conduct approximately 48 baseline interviews per month (24 interviews at each site per month) until 538 participants have completed the CTC intervention and 538 participants have completed the equal attention control intervention (*Timeline, Table 1* see below).

The elucidation study interviews will be offered to current study participants. Study 1 (HAV/HCV) is a quantitative survey that covers topics related to HAV risk (sanitation issues) and HCV treatment (Appendix N). Study 2 is qualitative in nature and addresses effects and withdrawal symptoms (Appendix O). Procedures in section 3.10 to 4.0 do not apply to the elucidation study.

3.10. Randomization. Following completion of the interview each participant will be randomly assigned (using urn,⁸⁹ see **Section 6.0**) to receive either the CTC intervention or the equal attention control nutrition intervention session, according to a computer-generated random numbers program. 3.11. Intervention fidelity and quality control. All intervention trainings will be audio-recorded. To ensure intervention fidelity, the Study Coordinator will listen to all recorded trainings for the first month and then a 10% random sample thereafter. The Study Coordinator will score intervention fidelity on a standardized form that will include a list of all intervention manual components. Interventionists will receive reports from these sessions. If interventionists score less than 95% fidelity on any session, they will be retrained by the Study Coordinator and tape recordings of their next sessions will be reviewed until a 95% fidelity rate is obtained. Given our past experience, training plan and oversight, we expect fidelity to rarely fall below 95%. Participants will also complete a short questionnaire on their satisfaction with the intervention session to which they were exposed (see **Appendix K**).

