3.12. Cohort maintenance and recapture strategies. We will use multiple proven strategies to retain cohort members at the 6-month and 12-month follow-up interviews. First, during enrollment for the proposed study, we will collect detailed tracking information, as described in **Section 3.8**. The Study Coordinator will enter tracking information into a Microsoft Access database on a password-protected laptop computer. We will use this information to locate participants who miss appointments. Second, participants will have a monthly check-in appointment with study staff, which will be held at field sites in the recruitment communities, and will receive a \$10 incentive for attending. At check-in, tracking information will be verified and updated. [name] has conducted two NIDA-funded cohort studies that compared the effectiveness of incentivized check-in appointments with that of standard tracking by outreach workers^{67,90} and found that paying each cohort member \$10 monthly yields much higher return rates and is less costly than relying on staff outreach alone. Third, we will use graduated incentives for the interviews: \$15 for the screener/baseline and \$20 for each of the 6-month and 12-month follow-up interviews. We will also allow the participants to return for up to one month past their study appointments. Study participants will continue to be eligible for the study throughout the follow-

up period even if they miss their check-in appointments. To minimize any potential participation biases during check-ins, research staff will only update contact information and not discuss any substantive topics.

3.13. Follow-up interviews at 6 and 12 months. Similar to baseline/screening interviews, 6- and 12- month follow-up interviews will be conducted using CAPI in a one-on-one session with a trained research interviewer. Participants will be remunerated \$20 for each follow-up interview they complete.

3.14. Timeline: As described in **Table 1**, below, following training and piloting, baseline data collection will commence in May 2016 and continue until December 2018.

Table 1. Project Timeline

	Year 01			Year 02			Year 03				Year 04					
Activity	Q3	Q4	Q1	Q2	Q3	Q4	Q1	Q2	Q3	Q4	Q1	Q2	Q3	Q4	Q1	Q2
Calendar year	'15	'15	'16	'16	'16	'16	'17	'17	'17	'17	'18	'18	'18	'18	'19	'19
RCT Baseline				Х	Х	Х	Х	Х	Х	Х						
6-month follow-up						Х	Х	Х	Х	Х	Х	Х				
12-month follow-up								Х	Х	Х	Х	Х	X	Х		

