3.17. Main independent measures will be intervention condition: CTC or equal attention control group for Aims 1 & 2. For Aim 3, we will also evaluate three injection initiation social learning risks as mediating variables. These items are intended to capture social learning constructs (i.e., observation of behavior, supportive interactions, and reinforcement) within the social processes of injection initiation. To capture observing, we will ask current PWID the following item: "In the past 6 months, have you injected drugs in front of someone who has never injected an illicit drug?" To capture interaction, we will ask "In the past 6 months have you explained or described how to inject to someone who has never injected an illicit drug (i.e., a noninjector)?" To measure reinforcement we will ask, "In the past 6 months, have you spoken positively about injecting with someone who has never injected an illicit drug?" Each item is a binary variable (Yes/No) where Yes denotes endorsing the injection initiation social learning risk assessed.

We will also collect IMB constructs related to injection initiation and sex risk. For the information construct, we will collect true or false knowledge items on sex-related HIV prevention provided by Kalichman, Simbayi and others^{5,6} and develop similar items for injection initiation risks. To develop injection initiation risk motivation and behavioral skill items we will follow procedures outlined by Kalichman, Simbayi and others.^{5,6} For sex-risk related motivation and behavioral skill items we will draw from existing studies.^{5,6} All injection initiation risk and sex-related IMB skill items will all be pilot tested. Psychometric properties of existing measures are known and acceptable, however, we will test both existing and new measures for their applicability to this study population. Drafts of all items are provided in the baseline survey (**Appendix H**).

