13.2. Sample size/ power analyses

Power calculations were estimated using Mplus by creating a Monte Carlo Simulation by generating a synthetic data set based on the expected parameter values, such as slopes, standard errors, and correlations among measured variables, for the anticipated treatment effect.^{113,114} Power was estimated assuming an intracluster correlation of 0.5, which is similar to our previous NIDA-funded studies.^{105,112,115} Statistical tests were two-sided, allowing detection of effects in either direction, and an alpha of .05 and power at 80%, corresponding to moderate effect sizes. Because the outcome is a count (i.e., Poisson), standard errors were estimated as non-normal via a sandwich estimator in Mplus.¹¹⁶ Co-Is [name] and [name] found that the number of participants who initiated people into injection was halved at follow-up.⁷ Preliminary data from MPIs [name] and [name]'s study in LA and SF indicated that 809 active PWID were found to have initiated 431 people in the past year. Using the same proportion, we expect that 573 people would be initiated by our proposed sample size of 1,076 participants at baseline (286 in each arm). If the number of people initiated by intervention group participants is halved, as suggested by [name] and [name]'s pilot data, that would represent a reduction of 143 people not being initiated into injection.

We also calculated the effect under different assumptions of attrition, subgroups (e.g., 25% Latino), sex, and age. For brevity, we illustrate power for primary outcome and most conservative—changes in the number of injection initiation events. We also account for 25% attrition—our worst-case scenario. To test the three hypotheses given our alpha and power specifications, we would need a baseline recruitment of 1,076 (n=538 per condition). We will recruit 1,076 participants to achieve the final sample of approximately 800 at the 12-month data point. The sample power for Cohen's effect sizes for small (2 percentage point difference), medium (5% difference) and large (10%–15% difference) effect sizes are plotted in **Figure 4**, revealing that after

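### Section 5.3 lets randomised participants who miss their session be asked to leave the study, and nothing in the available text keeps them in the 6- and 12-month interviews; separately, 1,076 counts different people in different sections

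*Combined protocol and SAP*

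**What the plan says.** **Order of events.** Section 3.10 places allocation between the baseline interview and the session: "Following completion of the interview each participant will be randomly assigned".

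**Withdrawal.** Section 5.3: "Participants who unable to complete either the experimental or control condition intervention may be asked to withdraw from the study". It adds: "Each participant will be given at least 2 opportunities to complete the one-hour educational session to which they were assigned". The withdrawal is from the study, not only from the session.

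**Retention.** The nearest protective text is in 3.12: "Study participants will continue to be eligible for the study throughout" follow-up. That sentence concerns missed monthly check-ins and does not mention the session.

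**Analysis.** Section 3.17 says that the main independent measure "will be intervention condition: CTC or equal attention control group". Section 13.1 fits treatment condition as a covariate, checks for differential loss between arms, and allows fidelity to enter as a covariate. Section 13.3 censors at loss to follow-up, adds a separate intention-to-treat analysis that gives dropouts an unfavourable result, and mentions pattern-mixture models and sensitivity analyses. Neither section names a primary analysis set.

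**The count.** Section 2.0: "N=1,076) will be randomly assigned to receive CTC or an equal attention control condition". Section 13.2: "we would need a baseline recruitment of 1,076 (n=538 per condition". Section 3.9 continues baseline interviewing "until 538 participants have completed the CTC intervention and 538 participants have completed the equal attention control intervention".

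**The concern.** Not completing the session happens after randomisation. If staff use 5.3, the people removed are a selected group, and their 6- and 12-month counts are not collected. A model that keeps the assigned arm as its covariate cannot include outcomes that do not exist. Imputation or pattern-mixture modelling can make assumptions about those outcomes but cannot recover them.

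Differential non-completion is plausible, though not documented. CTC asks participants to talk about initiating other people, and the control session is about healthy eating. If the people who stop differ by arm in how often they initiate others, the two groups left are no longer the randomised groups.

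The count is a separate matter. The same 1,076 cannot be both everyone randomised and everyone who completed a session unless non-completion is zero, and 5.3 exists because some is foreseen.

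**Working it through.** **1. Reproduce the plan's count.** Section 13.2 gives 25% attrition and about 800 at 12 months. 800 / 0.75 = 1,067, close to 1,076. In reverse, 1,076 × 0.75 = 807. So 1,076 behaves as a baseline total. The completer target in 3.9 gives the same figure: 538 + 538 = 1,076.

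**2. Bias under no true effect.** The plan gives no non-completion rates, so these are assumptions. Let q1 and q0 be non-completion in CTC and control, and k the non-completers' initiation rate relative to completers, the same in both arms. Every non-completer is taken to be withdrawn. With equal overall rates in the two arms, the completers show

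apparent rate ratio = [(1 − q0) + q0·k] / [(1 − q1) + q1·k]

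| k | q1 = 10%, q0 = 5% | q1 = 5%, q0 = 10% |
|---|---|---|
| 0.5 | 0.975/0.950 = 1.03 | 0.950/0.975 = 0.97 |
| 1 | 1.00 | 1.00 |
| 2 | 1.05/1.10 = 0.95 | 1.10/1.05 = 1.05 |
| 3 | 1.10/1.20 = 0.92 | 1.20/1.10 = 1.09 |

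With q1 = q0 the ratio is 1.00 for every k.

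**3. What the two meanings of 1,076 imply**, at an assumed 5% and 10% non-completion:
- If 1,076 must complete, the number randomised is 1,076/0.95 = 1,133 or 1,076/0.90 = 1,196.
- If 1,076 are randomised and all are followed, 12-month data come from 1,076 × 0.75 = 807.
- If 1,076 are randomised and withdrawals are neither replaced nor part of the 25%, the figure is 1,076 × 0.95 × 0.75 = 767 or 1,076 × 0.90 × 0.75 = 726.

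**4. Power.** The plan's simulation cannot be rebuilt because its parameters are not given. As an approximation, scale from its stated 0.82 at 800 (small effect): z = 0.915 + 1.960 = 2.875, and power = Φ(2.875 × f × √(n/800) − 1.960), where f is the share of the effect kept. If non-completers get no benefit and have the same underlying rate, following everyone gives f = 1 − q.

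| Option | 5% non-completion | 10% non-completion |
|---|---|---|
| Withdraw, not replaced, on top of the 25% (f = 1) | n = 767: 0.80 | n = 726: 0.78 |
| Randomise 1,076, follow all | n = 807, f = 0.95: 0.78 | n = 807, f = 0.90: 0.74 |
| Keep 1,076 completers, follow all randomised | n = 1,133 × 0.75 ≈ 850, f = 0.95: 0.80 | n = 1,196 × 0.75 = 897, f = 0.90: 0.78 |

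**5. Dilution of the rate ratio.** With a true 0.50 in completers, no benefit in non-completers and equal q in both arms, the ratio is [(1 − q)·0.5 + q·k] / [(1 − q) + q·k]. With k = 1 it is 0.525 at 5% and 0.55 at 10%. At 10% it runs from 0.526 (k = 0.5) to 0.625 (k = 3).

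**The case against.** The rule may hardly ever be used. It says may, it follows at least two chances at a single one-hour session, and it applies to both arms. Nothing in the documents suggests that non-completion would be common or unequal. Under equal and similar non-completion the bias is nil, and the unequal scenarios above give shifts that are small beside the halving the plan expects. All of this stands, and it limits the severity.

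The analysis is also largely by assigned condition. A reader might infer that a completer-only analysis is planned. The documents do not support that: no such analysis appears, 13.1 uses the treatment covariate, its Aim 3 text refers to randomised status, and imperfect delivery is handled through fidelity checks. What remains is that no primary analysis set is named, intention-to-treat appears only as a separate analysis, and none of this collects the missing interviews.

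A reader might also infer that the number to randomise is undefined, or that the trial will fall short. Neither follows. Sections 2.0 and 13.2 both set 1,076, and the completer rule in 3.9 could only raise the number randomised. The fall to 767 or 726 needs withdrawals to be unreplaced and additional to an attrition figure that the plan calls its worst case.

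Finally, following everyone has a price. Under the dilution assumption, randomising 1,076 and analysing all gives lower approximate power than withdrawing non-completers. That is fair and should be disclosed, but it does not make excluding them unbiased.

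**Conclusion.** The point holds in a limited form. Section 5.3 permits loss of outcomes on a post-randomisation event, and no available text keeps non-completers in follow-up. Some protocol text between 7.2 and the data safety monitoring board description, and the consent forms, were not available, so a safeguard there cannot be ruled out.

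Size and direction are unknown because no non-completion rate is given. The range of 0.92 to 1.09 rests wholly on assumed rates and on withdrawal of every non-completer. It would matter mainly if the true effect is small. It does not show that the trial will be biased, or in which direction.

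The meaning of 1,076 in 3.9 does not agree with 2.0 and 13.2. The documents support asking for reconciliation, not a choice between them. Severity: minor to moderate.

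**What to change.** - **Section 5.3:** state that not completing the session is not in itself a reason to end follow-up, and that these participants are still invited to the 6- and 12-month interviews.
- **Section 13.1:** state that the primary comparison includes all randomised participants as assigned, using all observed counts, and that session completion will be reported by arm.
- **Sections 2.0, 3.9 and 13.2:** reconcile whether 538 per arm means randomised or session completed, and make the stated power reflect the choice together with follow-up of everyone randomised.

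The cost is wording, some staff time to track non-completers, and dilution. Under the assumptions above, approximate power at 5-10% non-completion is 0.78 to 0.74 if 1,076 are randomised, or 0.80 to 0.78 if the completer target is kept. The second option means randomising 1,133 to 1,196 people, against about 1,200 planned for screening in 3.2, with the added interviews and incentives. Under the first, little or no extra incentive cost arises.

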6.0 STRATIFICATION/DESCRIPTIVE FACTORS/RANDOMIZATION SCHEME

- 6.1 Stratification factors. Not applicable.
- 6.2 Descriptive factors. Based on prior studies with PWID, we anticipate the following characteristics: The majority will be over the age of 50, roughly a third will be white, a third will be African American, and 25% will be Latino. About 25% will be female. The vast majority will be heroin injectors although a third will also report methamphetamine use, and 10% will report cocaine and opiate prescription injection in the last 30 days.
- 6.3 For participants in the RCT, randomization will be accomplished using urn. Urn randomization is an adaptive biased-coin randomization method.⁸⁹ In brief, it means you not only replace the ball that is chosen out of a hat (for example: blue for experimental and red for control condition), but you add a ball from the opposite color as well. The urn design forces balance for studies

with a large number of confounders as it approaches complete randomization and full balance as the size of the trial increases. Consequently, the urn design is not as vulnerable to experimental bias as are other restricted randomization procedures.

7.0 STUDY AGENT ADMINISTRATION OR INTERVENTION AND TOXICITY MANAGEMENT PLAN

7.1. CTC can be viewed as integration of social learning theory and the Information-Motivation-Behavioral skill model (IMB). CTC uses social learning theory to explain how active PWID might influence directly (by assisting in first injection) and indirectly (through promoting and exposing non-injectors to injection) injection initiation among non-injectors.^{1,2} It uses IMB to *promote* behavior change among active PWID by providing them with information, motivation and behavioral skills related to direct and indirect influences of injection initiation.^{3,4} **Figure 2**, graphically illustrates these theories are integrated within CTC.

Figure 2. Integration of IMB skill model with social learning theory for purposes of reducing injection initiation as operationalized in CTC.

In the figure, the IMB model constructs of information and motivation (the 2 left-most bubbles) reinforce each other; enhance behavioral skills acquisition; and contribute to reductions in injection initiation social learning risk (top bubble on the right), requests for injection initiation, and actual injection initiation episodes (bubbles below social learning risk bubble). CTC modules are listed within IMB construct bubbles. We expect IMB-related changes to influence social learning risk, including interactions with (describing how to inject), observations/exposure to injection (injecting in front of non-injectors), and reinforcement (encouraging injection drug use). Reductions in social learning risk should lead to lower incidence of both requests to initiate and actual injection initiation episodes (behavioral experimentation). The integrated model targets the injection drug use, by providing information, motivation, and behavioral skills to reduce injecting in front of, describing injection to, and speaking positively about injecting to non-injectors.⁴⁵⁻⁵⁶ **Aim 1** will test the impact of CTC on counts of injection episodes, while **Aim 2** tests CTC effect on injection initiation request. **Aim 3** will explore the theoretically and empirically supported mediational mechanism between CTC, social learning risk, and request for and episodes of injection initiation.

7.1.1. The Change the Cycle intervention

The CTC intervention is an hour-long, guided conversation with a trained interventionist. Copies of the Peer Educator Handbook and Intervention Guide that were developed by Drs. [name] and [name] and adapted for this study are included in *Appendices A* and *B*, respectively. Using the Intervention Guide, the interventionist introduces and summarizes CTC goals and then delivers the following seven modules in one session:

- 1. Discussion of the participant's own experience the first time they injected, including when it occurred, motivations for initiation, who was present, and feelings about initiation (~5 minutes).
- 2. Discussion of the participant's experiences of initiating others, focusing on the participant's thoughts about the experience, the relationship to the person they initiated, the context of initiation, and descriptions of those times they refused to initiate someone (~5 minutes).
- 3. The participant's perceptions of the health, legal, and social risks of initiating non-injectors (~5 minutes).
- 4. The participant's perceptions of the health, legal, and social risks of initiation for themselves (~5 minutes).
- Identification of aspects of the participant's own behavior and the behaviors of other PWID that may
 promote injecting to non-injectors and linking those behaviors back to the participant's own initiation
 experience (~10 min). Includes discussion of: (A) Talking about the physical benefits of injecting in front of

injection-naive people; (B) Talking about the economic benefits of injecting compared with using drugs other ways (e.g., snorting, smoking); and (C) Describing how preparing drugs for injection in front of non-injectors might inadvertently promote injection initiation.

- 6. Skill-building session to prevent future initiation events. We have developed 9 different scenarios covering a range of possible events based on the relationship and drug use characteristics of the participant.
- 7. A safer injection education session focusing on topics such as hygiene, risks of sharing needles and other injection equipment, rotating veins to avoid abscesses, etc. (~5 min).

7.1.2 The equal attention control intervention. To ensure that the participants in the intervention and control groups are having the same study-related experiences, control participants will receive an intervention that mimics the experience but differs in content. The equal attention control intervention will focus on improving health eating among PWID. We have developed a single-session, 60- minute Information-Motivation-Behavioral (IMB) skills-based intervention addressing healthy eating (**Appendix J**). Similar to the CTC, the healthy eating intervention uses a one-on-one guided conversation between the interventionist and the participant. The intervention addresses (1) information about current eating patterns and recommendations for healthy alternatives (20 minutes), (2) motivations for improving healthy eating by providing feedback to participants on personal responsibility, a menu of alternative change options, a decision balance exercise, and eating goal setting (10 minutes), and (3) Behavioral Self-Management Component (30 minutes) that covers eating scenarios, participant responses, and healthy alternatives to the scenario and the participants feedback. The participant is also remunerated \$15 for completing the session.

7.2. *Elucidation studies:* The elucidation studies are pilot interviews. We anticipate interviewing 60 PWID for study 1 and 40 PWID for study 2.

